The in-person rehabilitation control group will have a cuff applied but inflated to a value of 20-30 mmHg, which will not occlude blood flow to the affected extremity.

The rehabilitation protocol would be performed for a total of 8-12 weeks. Postoperative rehabilitation will be divided into a non-weightbearing and weightbearing/strength-building phase as guided by surgeon discretion after meniscus repair. Rehabilitation would begin within 3-7 days after meniscus repair. Of note, in the non-weightbearing phase, low-intensity neuromuscular

electrical stimulation (NMES) will be combined with BFR [20]. Non-postoperative patients will be progressed through standardized exercises according to patient strength and tolerance at the discretion of the physical therapist, as outlined in Appendix 3.

For both the in-person and telehealth rehabilitation groups, 4 sets of 30-15-15-15 repetitions would be performed per exercise with 15-30s rest between sets while the cuff is inflated. Exercises will be progressive loaded per physical therapist discretion with a goal of an exercise intensity of 20-30% 1-RM with 30-45s rest between sets. Occlusion will be maintained throughout the inter-set rest time, but patients will be given non-occlusive rest between exercises if desired by the patient or as guided by the physical therapist between exercise demonstrations and set-up. The reperfusion timer associated with the tourniquet system will ensure adequate reperfusion time between pressurization cycles. Postoperative patients will attend physical therapy sessions twice a week for the non-weightbearing period (typically up to six weeks) and once-to-twice a week during the weightbearing phase. Non-postoperative participants will meet with their physical therapist once-to-twice per week through the entire study period. RPE would be evaluated to strive for a goal RPE of 7-8 during the rehabilitation session.

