7.10 STANDARD CLINICAL PRACTICE: To what extent, if any, do the planned research procedures differ from the care that people would otherwise receive at this institution or the study site if not being done locally:

The research procedure and protocol involves minimal change to standard clinical practice. The primary difference is that the intervention group would be performing the same exercises as the standard-of-care rehabilitation control group with the addition of the blood pressure cuff for blood flow restriction training applied to an occlusive pressure. For the in-person rehabilitation control group will have the cuff applied, but inflated only to 20-30 mmHg to not occlude blood flow. The International Knee Documentation Committee (IKDC) survey is not routinely administered in our orthopaedic or physical therapy clinic visits, but would be administered to both groups as a measure of patient-reported outcomes.

7.11 INSTRUMENTS: List all questionnaires, surveys, interview, or focus group guides that will be used for this study:

The International Knee Documentation Committee (IKDC) survey will be administered to patients in both study arms at 6-week, 3-month, and 6-month clinic visits or electronically.

Attach any unpublished instruments in the 'Other Study Documents' section of the Initial Review Submission Packet form after completing the study application. Published instruments should NOT be attached.

7.12 * BIOSPECIMEN COLLECTION: Are you drawing any blood or collecting other biosamples (e.g. tissue, buccal swabs, urine, saliva, hair, etc.) for analysis under this protocol and/or storage for future research: (REQUIRED)

☐ Yes ☒ No

7.13 STATISTICAL METHODS: Briefly summarize the methods and types of analyses that will be performed:

Power Analysis:

Aim 1 – Knee Extension

In a previously published study by Bowman et al., knee extension torque in this RCT's BFR group increased by 11% +/- 13 and the knee extension torque in the control group increased by 3% +/- 9 [5]. Using this data, the effect size expected is 0.72. Utilizing a goal of 0.8 power, alpha 0.05, and equal enrollment between groups, power analysis reveals a sample size goal of 50 patients (25 per group) for patients following meniscus repairs and 25 patients with additional orthopaedic knee conditions.

Aim 2 – Y-balance testing & IKDC

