In Hughes et al. recent study comparing BFR to traditional heavy load resistance training in post-surgery ACL patients, Y-balance testing was most similar in the anterior direction, with scores normalized to leg length 32.9 +/- 9.7 for the BFR group and 17.5 +/- 6.7 in the traditional group [26]. Using this data, the effect size expected is 2.23. Utilizing a goal of 0.8 power, alpha 0.05, and equal enrollment between groups, power analysis reveals a sample size goal of 8 patients (4 per group) for Y-balance testing. For IKDC, overall mean difference in that paper was 35.63 +/- 7.06 for the BFR group and 23.33 +/- 8.76 for the traditional group [26]. The effect size with this data is 1.54. Utilizing a goal of 0.8 power, alpha 0.05, and equal enrollment between groups, power analysis reveals a sample size goal of 14 total patients for IKDC (7 per group). Of note, Irrgang et al. described the international knee documentation committee (IKDC) subjective knee form and determined the value for a true change in score of 9.0 points which was achieved in that study [27].

Overall, the power analysis is most limited by knee extension (75 total patients or 25 per group). To account for dropout, canceled surgeries, and patients who are unable to make all of their physical therapy visits, we aim to enroll 40% more, or a goal of **105 patients total (35 per group)**.

Statistical Analysis:

Statistical analysis will be performed comparing groups utilizing non-normative distribution analyses after obtainment of data. The alpha value for significance will be set to 0.05. Confidence intervals will be established on mean strength measures and thigh circumferences. For functional measures and IKDC survey, average scores and standard deviations will be utilized.

7.14 REFERENCES: List only the 5-10 most relevant references (a separate bibliography can be attached for reference purposes if this study involves novel approaches, agents, or an emerging technology that the IRB may not be familiar with):

Please see a full separate bibliography attached. Most relevant references are below:

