12.0 Risks and Benefits

12.1 RESEARCH-RELATED RISKS: Check if your study involves any of these specific research-related risks to participants that may need to be disclosed in the consent form:

- ☐ For interventional studies, risk that the regimen may be more harmful or less effective than other available interventions
- ☐ Risks associated with radiation exposure for imaging studies specifically for research purposes
- ☐ Risks associated with the administration of contrast agent for imaging studies
- ☐ Risks associated with withholding of treatment or discontinuation of current treatment (e.g., washout period is required by the study protocol)
- ☐ For randomized, placebo-controlled trials, possible temporary or permanent health consequences from the deprivation of effective therapies during the placebo administration period
- ☐ For studies involving a sham surgical procedure, the risk that participants may experience increased morbidity without the possibility of benefit
- ☐ Risks associated with modification or extension of a surgical procedure primarily for research purposes (e.g. risks associated with prolonging anesthesia, time in the operating room, etc.)
- ☒ Risk of pain or physical discomfort caused by the research intervention
- ☐ Possible personal discomfort due to sensitive topics (stress, embarrassment, trauma)

12.2 * RISKS: Describe any anticipated risks and discomforts not listed above: (REQUIRED)

Patients may have difficulty tolerating the BFR training. Although prior studies do not report much patient discomfort, we aim for an RPE of 7-8. This may not be tolerable for all patients, and if it is not, it is important to note this when planning for a future rehabilitation protocol. We have accounted for potential patient dropout if patients later decide to decline the BFR protocol.

With meniscus injuries and with post-operative immobilization to protect surgical repair, patients may experience quadriceps atrophy. This is a normal result of immobilization and not related to the study intervention. The goal of the study intervention is to seek a way to minimize this risk using the BFR training.

Risks and side effects related to the blood flow restriction training include those which are:

Likely

- Soreness during or after activity
- Muscle fatigue

Less Likely

- Pain at the site of the blood pressure tourniquet/cuff

Rare but serious

- Blood clots

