Data collection will be monitored by the clinical research coordinator. Data will be collected via a UCSF REDCap database which is HIPAA-compliant and secure. The research coordinator will be in charge of the database and blinded data will be presented to the researchers for data analysis and review. Study progress will be monitored by the research coordinator and the PI, including the total number of enrollees, surgical dates, and completion of physical therapy sessions and post-operative follow-up. Study progress will be monitored monthly at the UCSF Sports Medicine monthly research meeting.

In addition to data for the purposes of analysis (such as functional outcomes and measures taken in the physical therapy sessions), adverse events, unanticipated problems, and complications will be reviewed by the physical therapists, the PI, and the research coordinator. All of these complications will be reviewed immediately by the study group with immediate notification to the PI and clinical research coordinator.

Interim data analysis will be conducted once over 50% of the patients have been enrolled and completed their post-operative follow-up appointments including functional outcome scores.

Patients reserve the right to withdraw from the study at any time. Patients will be removed from the study intervention if they are unable to tolerate the discomfort or are unable to attend the appropriate number of physical therapy sessions. The study protocol will be re-evaluated at any time of adverse events or complications from the intervention and the study will be stopped if there are concerns for unanticipated risks.

13.2 * DATA AND SAFETY MONITORING BOARD (DSMB): (REQUIRED) Will a Data and Safety Monitoring Board (DSMB) be established:

- ☐ Yes
☒ No

Guidelines

A Data and Safety Monitoring Board (DSMB) or Data Monitoring Committee (DMC) is a formal, independent committee that is specifically established to conduct interim monitoring, oversight and analysis of study information and data to assure the continuing safety, efficacy,

appropriateness, relevance, and integrity of the study.

The UCSF IRB reserves the right to request a DSMB/DMC for any study. However, the following are factors that the IRB will consider when making this determination:

- There is a significant likelihood of a serious adverse event to subjects
- The study is conducted at multiple sites and the level of risk is greater than minimal

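### Non-adherence to BFR is counted as loss, with no commitment to keep measuring and analysing those patients, so the randomised comparison could become a completers comparison that favours BFR

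*Combined protocol and SAP*

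**What the plan says.** Section 7.13 (repeated in 9.3) takes 25 per group from the power calculation and adds 40%, giving 35 per randomised group. The reason given is "To account for dropout, canceled surgeries, and patients who are unable to make all of their physical therapy visits". Missing data and non-adherence share one allowance.

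Section 12.2 acknowledges that some patients may not tolerate the training and adds: "We have accounted for potential patient dropout if patients later decide to decline the BFR protocol". Section 13.1 says patients will be "removed from the study intervention if they are unable to tolerate the discomfort or are unable to attend the appropriate number" of therapy sessions. The number of sessions is not defined, and nothing is said about further assessment or analysis of these patients.

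The two randomised arms differ in the cuff. Under 7.9, the BFR cuff is set to 80% of limb occlusion pressure, while the in-person "control group will have a cuff applied but inflated to a value of 20-30 mmHg".

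Strength and circumference are measured by physical therapists, at therapy sessions according to 7.2. Functional tests and IKDC belong to the clinic follow-up at 6 weeks, 3 months and 6 months (7.9). The statistical analysis paragraph of 7.13 names no analysis set and no missing-data method. No section says when randomisation takes place relative to surgery.

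**The concern.** A missed therapy visit, or a decision to stop the cuff, is non-adherence. It does not by itself remove an outcome. Enlarging the sample for it makes most sense if such patients are not expected among the 25 per group who carry the power. Read with 12.2 and 13.1, the plan appears to expect that patients who stop will be gone from the data.

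Where strength is measured makes this more than a gap in wording. A patient who stops attending therapy also stops being present for the dynamometer reading, so following the plan as written would lose the strength outcome for that patient.

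Intolerance of occlusion falls mainly on the BFR arm. If the patients who cannot tolerate it are also the weaker ones, the BFR patients left at the end are a selected, stronger group. The comparison would then lose the protection of randomisation in the direction of the study hypothesis.

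**Working it through.** **1. The plan's own sample size.** The inputs in 7.13 are: "BFR group increased by 11% +/- 13 and the knee extension torque in the control group increased by 3% +/- 9"; "Using this data, the effect size expected is 0.72"; and "Utilizing a goal of 0.8 power, alpha 0.05, and equal enrollment between groups".

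- Pooled SD = sqrt((13² + 9²)/2) = sqrt(125) = 11.18. Effect size = (11 − 3)/11.18 = 0.716, which agrees with 0.72.
- A t-test with 80% power at alpha 0.05 needs 24.9 per group one-sided, i.e. 25, which matches the plan. Two-sided it needs 31.6, i.e. 32. The plan does not state sidedness; that is a separate point.
- Inflation: 25 × 1.40 = 35 per group; 75 × 1.40 = 105 in total. Both match.
- The loss that this covers is 1 − 25/35 = 28.6%, or 10 patients per randomised group.

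So 25 per group is what remains after the allowance for missed visits and declined BFR is used up. That fits a count of completers, although the plan does not use the word.

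**2. Bias if stoppers are lost.** All of the following are assumptions: no true effect; 35 per arm; each arm loses its least tolerant patients; tolerance and final strength are bivariate normal with correlation ρ. If a fraction f is lost, the mean strength of those who remain rises by ρ × h(f), where h(f) = φ(z)/(1 − f) and z is the f-quantile of the standard normal. The bias is ρ × [h(f in BFR) − h(f in control)].

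- h(2/35) = 0.1146/0.9429 = 0.122
- h(5/35) = 0.2256/0.8571 = 0.263
- h(10/35) = 0.3399/0.7143 = 0.476

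| Lost, BFR v control | Difference in h | Bias in SD at ρ = 0.3 / 0.5 / 0.7 | Two-sided false-positive rate (simulated) |
|---|---|---|---|
| 10 v 2 | 0.354 | 0.11 / 0.18 / 0.25 | 7% / 11% / 18% |
| 5 v 2 | 0.142 | 0.04 / 0.07 / 0.10 | 5.3% / 6.4-6.6% / 8.4% |
| Equal losses | 0 | 0 / 0 / 0 | not inflated |

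With ρ = 0 the bias is zero for any split of losses. On the 11.18-point scale, 5 v 2 is about 0.5 to 1.1 percentage points (0.0425 × 11.18 to 0.099 × 11.18), and 10 v 2 is about 1.2 to 2.8 (0.106 × 11.18 to 0.248 × 11.18). The planned difference is 8.

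**3. Power if everyone is analysed as randomised.** Assume that a fraction f of the BFR arm stops and then responds like controls, with the SD unchanged. The effect size is 8(1 − f)/11.18. With 35 per group and two-sided alpha 0.05:

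- f = 0: 8/11.18 = 0.716, power 0.84
- f = 10%: 7.2/11.18 = 0.644, power 0.76
- f = 20%: 6.4/11.18 = 0.572, power 0.66

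**The case against.** A reader might infer that patients who stop will be replaced, that the primary comparison is per-protocol, and that it is biased towards BFR. The documents do not support any of these as fact.

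- There is no replacement rule. Enrolment is enlarged in advance, and enlarging it excludes nobody.
- No section excludes anyone from analysis. The analysis set is undefined, and 13.1 separates withdrawing from the study from being taken off the intervention.
- Cancelled surgery comes before any cuff use, so it cannot reflect tolerance. If assignment follows surgery, it cannot enter the comparison at all.
- Missed visits can occur in either arm, because the visit schedule and exertion target in 7.9 are not arm-specific. Only intolerance of occlusion is.
- The 10 v 2 case is near a worst case. It gives the whole BFR allowance to intolerance, although that allowance also covers cancelled surgery, missed visits and ordinary dropout. Section 12.2 says prior studies report little discomfort and lists cuff pain as less likely.

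All of this stands, and it limits the claim to a conditional risk. The gap remains: three places treat non-adherence as loss, none keeps these patients in the data, and strength is collected where non-attenders will not be.

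**Conclusion.** The concern holds as a conditional risk in the randomised meniscus-repair trial. The plan counts non-adherence as loss and gives no assurance that patients who stop are measured or analysed, which leads towards a completers comparison that could favour BFR. The bias is small if few patients stop and material if the BFR allowance is used up by intolerance. It disappears if losses are equal and equally selective in the two arms, or unrelated to strength. The loss splits and the correlations are assumptions; the documents give neither. The rule on who counts should be fixed before data are seen, the more so because 13.1 plans an interim analysis.

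**What to change.** - **7.13:** state that the primary analysis includes every randomised patient who had the repair, in the assigned arm, whatever their cuff tolerance or attendance. Per-protocol results are supportive only.
- **13.1:** state that removal from the intervention does not end strength, functional or IKDC assessment, subject to the plan's existing safety exception for functional testing. Add a dynamometer measurement for patients who stop attending therapy, for example at a scheduled clinic visit. Those visits now carry functional tests and IKDC but no dynamometry, so this must be written in.
- **7.13 and 9.3:** divide the 40% allowance into patients with no outcome data and patients who are non-adherent but measured.
- **7.9:** state that the assignment is released after the repair and before the first rehabilitation session (which 7.9 places 3-7 days after surgery), so that cancelled surgeries do not enter the comparison.

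The cost is wording, a small measurement burden, and dilution of the effect by non-adherence. The dilution is not trivial: under the assumption in step 3, two-sided power at 35 per group falls from 0.84 to 0.76 or 0.66 if 10% or 20% stop BFR. The plan should state this alongside the sample size.

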We hypothesize that quadriceps extension force will be significantly higher in patients undergoing a rehabilitative protocol with BFR versus those undergoing standard rehabilitation.

7.2 AIMS: List the specific aims:

Aim 1: Evaluate the force production and strength of the affected extremity after BFR compared to those in the standard rehabilitation control group.

Hypothesis 1: Force production, as measured by peak force determined via hand-held dynamometer at 30 and 90 degrees of knee flexion for quadriceps and hamstrings, will be significantly higher after rehabilitation with incorporation of BFR relative to patients without BFR.

We will evaluate previously described primary measures including peak quadriceps/knee extension force and limb circumferences [8-11, 16, 17]. Rating of perceived exertion (RPE) will be measured during testing to ensure the patients are meeting appropriate standards of effort (RPE goal 7-8). Measurements would be taken weekly for up to 10 weeks post-operatively during assigned physical therapy sessions; these weekly measurements will be taken by trained physical therapists at UCSF who are blinded to the patient's treatment group.

Aim 2: Compare performance on functional outcome measures relative to those in standard-of-care rehabilitative protocols and secondarily evaluate patient-reported outcomes.

Hypothesis 2: Functional outcome scores, as measured via standard scoring for single leg squat and Ybalance tests, as well as patient-reported outcomes measured via the International Knee Documentation Committee (IKDC) score will be higher in those patients undergoing BFR training relative to those undergoing standard therapy.

We will compare functional and patient-reported outcome measures between the two groups to ascertain if there are clinical outcome differences after blood flow restriction training. Functional milestones evaluated include single leg squat test, 3-hop test, and Y-balance test. Patient-reported outcomes will be measured using the IKDC standard knee evaluation form at baseline and at the conclusion of the study period. By assessing the above aims, we seek to distinguish to see if BFR training helps mitigate quadriceps atrophy in patients with orthopaedic knee conditions. This readily available and non-invasive treatment may have the potential to greatly improve orthopaedic rehabilitation and limit the detrimental effects of post-operative atrophy and progressive muscular deconditioning.

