Approach: Standard functional milestones to be evaluated are: single leg squat test, 3-hop test, and Y-balance test. These tests are used routinely in the clinic to evaluate control of knee mechanics, proprioception, and balance. All of these are important functions to return to activity safely. These tests will be evaluated post-operatively at 6 weeks, 3 months, and 6 months. Rating of these tests will be performed by the surgeon in the clinic at the post-operative visits as has been previously described and on both the operative and non-operative extremities [21-24] and compared between groups using the associated scoring scales. **These functional tests are a part of standard post-operative and orthopaedic evaluation.**

In addition to these functional measures, patient reported outcomes would be measured at each clinic follow-up visit via the International Knee Documentation Committee (IKDC) outcome score, which has been demonstrated to demonstrate higher performance on measurements in those with meniscal injuries compared to Knee Injury and Osteoarthritis Outcome Score (KOOS) and Western Ontario and McMaster Universities Arthritis Index (WOMAC) [25]. This evaluation is subdivided into sections for symptoms, sports activities, and function and would be available for sub-analysis. The IKDC survey will be administered at 6-week, 3-month, and 6-month after beginning rehabilitation. **These IKDC surveys would be administered for research purposes and are not routinely used in post-operative or orthopaedic clinic visits.**

Expected Outcomes: We expect to see higher scores on functional measures in the BFR rehabilitation group compared to the standard of care group. Secondly, we anticipate better IKDC outcome score in those undergoing BFR training compared to standard therapy.

In summary,

(1) Patient-reported outcomes (PROs) will be taken prior to, during, and after rehabilitation

(2) Strength and thigh circumference measures will be taken and if the subject may not tolerate strength testing on the injured side, we will use the contralateral uninjured leg as a baseline for strength

(3) Functional testing will *not* be performed when the surgeon, physician, or physical therapist determine the patient would be at risk for further injury due to pain, weakness, instability, etc.

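### Aim 1 is sized on percent change in strength, but the analysis section names no change score or baseline adjustment, and the fallback rule mixes injured and uninjured legs in one baseline

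*Combined protocol and SAP*

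**What the plan says.** **Sizing.** Sections 7.13 and 9.3 base Aim 1 on a cited randomised trial in which the "BFR group increased by 11% +/- 13 and the knee extension torque in the control group increased by 3% +/- 9". The plan continues: "Using this data, the effect size expected is 0.72". With "Utilizing a goal of 0.8 power, alpha 0.05, and equal enrollment between groups" it arrives at 25 per group for the meniscus-repair cohort, raised by 40% to 35 per group enrolled.

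**Hypothesis and analysis.** Hypothesis 1 (7.2) is that peak dynamometer force will be higher after rehabilitation with BFR. The statistical analysis paragraph of 7.13 reads "Statistical analysis will be performed comparing groups utilizing non-normative distribution analyses after obtainment of data". It adds "The alpha value for significance will be set to 0.05" and promises confidence intervals on mean strength and thigh circumference. It gives no test, no choice between level, change and percent change, no primary visit among the weekly measurements, and no covariate.

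**Baseline strength.** The summary closing 7.9 says that if testing on the injured side is not tolerated, "we will use the contralateral uninjured leg as a baseline for strength".

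**IKDC.** Aim 2 (7.2) plans the "IKDC standard knee evaluation form at baseline and at the conclusion of the study period", and the 7.9 summary also places patient-reported outcomes before, during and after rehabilitation. The explicit schedules in 7.9 and 7.11 start later; 7.11 has the form "administered to patients in both study arms at 6-week, 3-month, and 6-month clinic visits or electronically".

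**The concern.** The SDs of 13 and 9 describe how much patients differ in their percent change. They do not describe how much patients differ in force. The trial takes men and women aged 18 to 60, and no normalisation of force is stated, so raw force may vary far more between people than percent change does. The effect size of 0.72 applies only if each patient's own starting strength enters the comparison, and 7.13 does not say that it will.

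If baseline is used, the fallback rule raises a second problem. For some patients, change would run from injured leg to injured leg. For others it would run from uninjured leg to injured leg, which includes the side-to-side deficit. Pooling the two as one percent change adds variance unrelated to treatment. Rehabilitation starts 3 to 7 days after repair (7.9), so the fallback may well be used.

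At stake are the power of the main comparison and a choice of analysis variable left open until the data are in hand.

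**Working it through.** **Inputs from the documents:** mean percent changes 11 and 3; SDs 13 and 9; alpha 0.05, sidedness not stated; power 0.80; 1:1 allocation; 25 per group analysed, 35 enrolled.

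**Assumptions, not in the documents:** between-person CV of baseline force 10% to 40%; share of patients on the fallback f; injured-leg deficit q. Powers in steps 2 to 4 come from simulation (5,000 trials per setting), with follow-up force = baseline × (1 + percent change/100).

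**1. The plan's own figure.**
- Pooled SD = √((13² + 9²)/2) = √125 = 11.18.
- d = (11 − 3)/11.18 = 0.716, agreeing with 0.72.
- n per group = 2(z_α + z_β)²/d². One-sided: 2(1.645 + 0.842)²/0.512 = 24.2, so 25, which matches. Two-sided: 2(1.960 + 0.842)²/0.512 = 30.7, so 31 (32 by the t distribution), which does not match.
- t-test power at 25 per group: 0.80 one-sided, 0.70 two-sided. The two-sided 0.70 is the reference for what follows.

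**2. A rank test, still on percent change from the patient's own injured leg.** Power at 25 per group is 0.66 two-sided and 0.78 one-sided, a cost of about 2 to 4 points. At 35 per group it is 0.82 two-sided.

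**3. Follow-up force compared without baseline.** With mean baseline set to 100, the variance of follow-up force is 100²·s² + (1 + m)²·(100·CV)² + (100·CV)²·s², where m and s are the mean and SD of percent change as fractions. At CV 20%:
- BFR: 169 + 492.8 + 6.8 = 668.6, SD 25.9.
- Control: 81 + 424.4 + 3.2 = 508.6, SD 22.6.
- Pooled SD = √588.6 = 24.3; d = 8/24.3 = 0.33.

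Two-sided power of the rank test:

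| CV | 25 per group | 35 per group |
|---|---|---|
| 10% | 0.40 | 0.52 |
| 15% | 0.26 | 0.36 |
| 20% | 0.18 | 0.25 |
| 30% | 0.11 | 0.15 |
| 40% | 0.09 | 0.10 |

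**4. Percent change from the mixed baseline.** For a fallback patient, percent change = (1 − q)(1 + m) − 1. At q = 30% this is −22.3% (BFR) and −27.9% (control), against +11% and +3% for the others: gaps of 33.3 and 30.9 points. With f = 25%:
- BFR variance = 0.75·169 + 0.25·0.7²·169 + 0.25·0.75·33.3² = 355, SD 18.9.
- Control variance = 0.75·81 + 0.25·0.7²·81 + 0.25·0.75·30.9² = 250, SD 15.8.
- Mean difference = 8 × (0.75 + 0.25 × 0.7) = 7.4.

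Two-sided rank-test power at 25 per group:

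| Share on fallback | q = 10% | q = 20% | q = 30% | q = 40% |
|---|---|---|---|---|
| 10% | 0.63 | 0.54 | 0.50 | 0.48 |
| 25% | 0.60 | 0.41 | 0.32 | 0.31 |
| 50% | 0.57 | 0.33 | 0.22 | 0.20 |
| 100% | 0.66 | 0.66 | 0.66 | 0.68 |

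The last row shows that the loss comes from mixing legs, not from using the uninjured leg as such.

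**5. Which remedy works.** With everyone's own injured-leg baseline available, adjusted analysis of log force has two-sided power of about 0.67 at 25 per group and 0.79 to 0.81 at 35. With f = 25% and q = 30% at 25 per group, adjusting for the mixed baseline alone gives only about 0.32. Let the leg-to-leg ratio also vary between patients by an assumed 5% to 15%, at CV 20%:
- Percent change from mixed legs: 0.32 to 0.34.
- Collected baseline plus an indicator for the leg: 0.61 to 0.48.
- Uninjured-leg covariate alone: 0.55 to 0.25. The lower end depends on the model; a check that placed the variation in the uninjured leg gave 0.33.

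**The case against.** The strongest reply is that 7.13 is brief rather than wrong. It does not say that raw follow-up force will be compared or that baseline will be ignored, and the fallback rule in 7.9 suggests that a baseline is meant to be used. That is correct. A reader might infer that the plan commits to an unadjusted rank comparison and has therefore lost most of its power. The documents do not support this, because a rank test on percent change is not excluded and would cost only 2 to 4 points.

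It is also fair that the two losses cannot be added. If baseline is ignored, the fallback leg has no effect on the comparison. If baseline is used, the raw-force loss does not arise. Every CV, deficit and fallback share is assumed, and mild values do little harm: 10% on the fallback with a 10% deficit leaves 0.63. Part of the gap from 0.80 is sidedness rather than choice of analysis.

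Finally, unequal use of the fallback might be thought to bias the arms. In the randomised cohort, if baseline is taken before treatment, such imbalance arises by chance and is already counted in the larger SD.

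What stands is that the quantity used for sizing is not carried into the analysis, and that the stated fallback rule, followed literally, makes percent change mean two different things.

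**Conclusion.** The point holds as a gap in specification with a conditional cost. Against 0.70 two-sided at 25 per group, power would be about 0.40 to 0.09 if follow-up force were compared without baseline (assumed CV 10% to 40%). Alternatively, it would be about 0.60 to 0.31 if percent change were computed across mixed legs (assumed 25% fallback, deficit 10% to 40%). One or the other could apply, not both, and neither applies if each patient's own injured-leg baseline is used throughout.

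In the randomised cohort the mixed baseline is mainly a loss of precision. A bias concern applies chiefly to the non-randomised cohort, where need for the fallback could differ systematically between groups. With a 30% deficit, a 10-point difference in fallback use would move the comparison by about 0.10 × 32 = 3 points, against a planned 8.

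The IKDC matter is a conflict of wording. A reader might infer that no baseline form is planned, but 7.2 and the 7.9 summary both plan one; the visit lists omit it.

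**What to change.** - **Strength (7.13).** State that follow-up log force is compared between arms at a named primary visit by ANCOVA or a mixed model, or by rank-ANCOVA if a rank method is preferred. Adjust for pre-rehabilitation strength and an indicator for whether that value came from the injured or uninjured leg. On the log scale the effect reads as a percent difference, in line with the sizing.
- **No change scores across legs.** State that change and percent change are not computed where baseline and follow-up come from different legs.
- **Circumference.** Adjust for its pre-rehabilitation value in the same way.
- **Optional.** Measure the uninjured leg before rehabilitation in everyone as an added covariate. It should not replace the injured-leg baseline where that was obtained. Follow-up values of the uninjured leg should not serve as a reference, since 7.1 and 7.5 cite BFR effects in the contralateral limb.
- **IKDC.** Add the pre-rehabilitation form to the lists in 7.9 and 7.11, and adjust IKDC for it.

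The cost is a few sentences in 7.13, one data field recording the leg tested, and the IKDC form already promised. The optional item adds a few minutes of dynamometry per patient. Baselines must be taken before rehabilitation starts, because they cannot be recovered later.
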